8.3.5 Follow-up after mAb TB31F administration (visits 4-12)

Follow-up visits will be carried out on an outpatient basis at the study center. Subject will be asked to examine the site of injection and record local signs and symptoms in their memory aid booklet (including bruising, erythema, swelling or induration) for seven days after injection as well as systemic symptoms throughout day 28. Subjects will also be asked to measure their body temperature in the mornings for 6 consecutive days after mAb TB31F administration. The subject diary will be reviewed at each study visit and used as a base for discussion of possible local and systemic adverse events or medication use. If the occurrence of an adverse event or use of medication is confirmed by the study physician, it is recorded in the clinical trial database. At the end of the study, the diary will be collected and kept as source data with the subject's study file. Follow-up visits *not* requiring blood collection for safety endpoints may be carried out by telephone, or at home, instead of at the clinical research center for subjects with suspected or confirmed SARS-CoV2 infection, until such time as they are considered no longer (potentially) contagious in accordance with current Radboudumc-wide guidelines. In such cases, it may not be possible to obtain blood samples for non-safety endpoints (PK, ADA & SMFA).

During the study period subjects will be instructed to call the trial physicians at any time if they experience severe symptoms or symptoms related to COVID-19. If clinically significant abnormalities are identified during the study, subjects may be asked to return to the study site for further evaluation, including clinical evaluation and repeat laboratory testing as warranted. The trial physician can decide to initiate any additional diagnostics (including safety laboratory evaluations) at all times. For unexpected laboratory abnormalities, the laboratory test will be repeated. If there is any ambiguity regarding the decision to include or exclude a volunteer, a trial physician will discuss the case with the local safety monitor.

8.3.6 Unscheduled visits

Subjects may need to present to the study center during operating hours for an unscheduled

visit should they experience any other AE that requires evaluation by the trial clinician. Data for any examinations performed on the subject at an unscheduled visit must be recorded in the eCRF. If an unscheduled visit is performed, the procedures for the next following visit should not be made earlier than scheduled above.

8.3.7 Medical history

The trial clinician will review the medical history of potential study subjects during the screening visit. The starting point will be a medical questionnaire the subjects have filled in before the screening. Particular attention will be paid to:

- Current or recent (within the previous two weeks) acute respiratory illness with or without fever, including symptoms associated with COVID-19;
- Recent receipt of immune globulin or other blood products, or injected corticosteroids or other immune modulator therapy within the previous six months;
- Hypersensitivity of any kind;
- Clinically relevant history of cardiovascular, renal, gastrointestinal, hematological, dermatological, endocrine, neurological or immunological diseases;
- Known or suspected immunologic function impairment of any kind and/or known HIV infection, hepatitis B or hepatitis C infection;
- Mental illness;
- Tobacco, alcohol, or drug use;
- Medication use in the past 6 months;
- For women, pregnancy and contraceptive use and/or history of surgical sterility. For males, use of contraception;

8.3.8 Physical Examination

A physical examination will be performed during screening, including the examination of general appearance, skin, neck, eyes, throat, lungs, heart, abdomen, back and extremities, and a routine vascular and neurological examination. At inclusion, a repeat measurement of body weight will be obtained. During follow-up visits a focused physical examination will be performed if deemed necessary by the trial physician.

8.3.9 Height and Weight

Height (cm) and body weight (to the nearest kilogram [kg] in indoor clothing, but without shoes) will be measured at the screening visit. Body mass index (BMI) will be calculated using the following formula: $BMI = \text{Body weight (kg)} / [\text{height (m)}]^2$ and converted to an integer. Body weight will be repeated at the inclusion visit to be used for the preparation of mAb TB31F in group 1 up till group 4.

8.3.10 Vital Signs

Vital signs including body temperature (degrees Celsius), blood pressure (BP, millimeters of mercury) and pulse measurements (beats per minute) will be recorded at the screening visit. Additional measurements will take place at the discretion of the physician.

Systolic and diastolic BP will be measured while the subject is sitting, with the back supported and both feet placed on the floor, using an automated validated device, with an appropriately sized cuff. In case the cuff sizes available are not large enough for the subject's arm circumference, a sphygmomanometer with an appropriately sized cuff may be used.

If vital signs are out-of-range at screening or baseline, the investigator may obtain two additional readings, so that a total of up to three consecutive assessments are made, with the subject seated quietly for approximately five minutes preceding each repeat assessment. At least the last reading must be within the normal range in order for the subject to qualify.

Temperature, blood pressure and pulse are measured as part of the physical examination at screening and inclusion. Additionally, subjects will be given a thermometer to measure their oral temperature on a daily basis for one week after TB31F administration, which they will collect in their study diaries.

8.3.11 Laboratory Evaluations

During the study, blood samples will be drawn for screening, safety and research purposes. The blood sampling schedule in the flowchart (section 8.3.18) shows the maximum amounts of blood that will be drawn. Following universal precautions, blood will be collected by venipuncture into vacutainer tubes. Blood specimens will be affixed with coded labels that link the specimen to the subject, specimen type, specimen collection date, and time-point. The specimen collection tube must be appropriate for the type of specimen required. The cumulative blood draw for each subject over the entire course of study participation is approximately 400mL.

Biological safety parameters will be measured on plasma or serum samples at the central laboratory of the RUMC. In the case where a laboratory assessment is outside the reference range, a decision regarding whether the result is of clinical significance or not shall be made by the investigator and shall be based, in part, upon the nature and degree of the observed abnormality. The assessment may first be repeated for confirmation. All abnormalities will be documented in the source documents, including clinical considerations.

Pharmacokinetic and functional analysis of transmission reduction activity

Pharmacokinetic (pK) sampling will establish the dose-response curve for each subject enrolled in this Phase 1 study. The serum concentrations of TB31F will be measured by an ELISA against a recombinant epitope R0.6C of the Pfs48/45 antigen at each sampling time point. Assessment of TB31F concentrations in the serum from subjects will be performed by the Human Immunology Laboratory at Imperial College London. Functional transmission-blocking activity will be determined at defined intervals as per protocol using SMFA assays performed at Radboudumc in Nijmegen the Netherlands

Complete Blood Count (CBC)

Complete hematology tests, including hemoglobin, hematocrit, red blood cell count, white blood cell count with differential (including neutrophils, basophiles, eosinophils, monocytes and

lymphocytes) and platelet count will be measured when appropriate. Complete hematology will be done at screening, at inclusion, at 24 hours and days 2, 7, 14, 21, 28 and 84.

Clinical Chemistry

Glucose will be measured only at screening. Alanine aminotransferase (ALT), aspartate aminotransferase (AST), creatinine, will be measured at screening, inclusion, at 24 hours and days 2, 7, 14, 21, 28 and 84.

8.3.12 Urine Toxicology analysis

A midstream urine sample (approx. 30ml) will be obtained, in order to avoid contamination with epithelial cells and sediments, to allow proper assessment. A toxicology screening will be performed at screening and at baseline. A positive test for amphetamines and cocaine is a reason for exclusion. A positive test for cannabis on the inclusion day prior to TB31F administration will also be a reason for exclusion.

8.3.13 Pregnancy Test

A midstream urine sample (approx. 30ml) will be obtained and assessed by commercially available hCG urine tests. This test will be done at screening (visit 1) and inclusion (visit 2).

8.3.14 Discontinuation of study procedures

Participants have the right to decline study procedures for any reason and at any time during the study. If a subject declines study procedures, this will be recorded as a study deviation and the reason will be clearly documented in the source document. The subject will be encouraged to complete all remaining safety related follow-up visits and procedures through the entire study period, including unscheduled visits. The reason for all discontinuations will be documented in source documents and the eCRF.

8.3.15 Standard Membrane Feeding Assay

Samples for SMFA will be collected from all subjects. Sera and/or purified IgG prepared from each serum will be used in the SMFA. Samples will be frozen until SMFA is planned. SMFA assays will be performed at both Radboudumc (The Netherlands) and the Laboratory of Malaria and Vector Research (LMVR), NIH USA, using a qualified standard membrane feeding assays using serum from subjects in cultures with *P. falciparum* and *Anopheles stephensi* mosquitoes.

8.3.16 Pharmacokinetic laboratory assay

A qualified ELISA assay developed at the Human Immunology Laboratory of Imperial College London will be used to measure the pharmacokinetics of TB31F in subjects' sera. The ELISA will detect TB31F in sera against its target antigenic epitope (R0.6C) at 12 time points as shown in section 8.3.18.

8.3.17 Safety Assessments

Planned safety assessments will provide the data for active monitoring of investigational product safety during conduct of the trial and for the primary reactogenicity and safety endpoints. Subjects will be observed directly for 60 minutes following product administration. AEs will be recorded prior to infusion, EOI, 6 and 24 hours, and at all follow-up visits. Clinical laboratory results assessed as AEs will be scored for severity using adapted Food and Drug Administration Toxicity Tables (see Appendix 1).

8.3.18 Time and Event procedures: TB31F

Type of contact	Visit 1 (Screening)	Visit 2	Visit 3					Visit 4	Visit 5	Visit 5a*	Visit 6	Visit 6a*	Visit 7	Visit 8	Visit 9	Visit 10	Visit 11
Study Day	D-84 to D-1	D-1	D0	D0	D0	D0	D0	D1	D2	D4	D7	D10	D14	D21	D28	D56	D84
Time after D0 infusion			pre	EOI	1hr	3hr	6hr	24hr	48hr	96hr	Wk1	Wk1,5	Wk2	Wk3	Wk4	Wk8	Wk12
Informed consent	•																
Inclusion/exclusion criteria	•	•															
Demographic data and medical history	•																
Physical examination ¹	• ¹	• ¹	• ¹	• ¹	• ¹	• ¹	• ¹	• ¹	• ¹	• ¹	• ¹	• ¹	• ¹	• ¹	• ¹	• ¹	
Height and weight measurement	• ¹	• ¹															
Blood pressure, temperature, pulse ²	•	• ²															
Record any concomitant medications	•	•	•					•	•	•	•	•	•	•	•	•	•
HIV, HBV, HCV (3,5mL)	•																
Pregnancy test (urine)	•	•															
Drugs screening (urine)	•	•															
Distribution of emergency notification card	•																
Distribution of memory aid card	•																
COVID-19 diagnostics ³	•																
TB31F administration			•														
Solicited local AEs (days 0-7)			•	•				•	•	•		•					
Solicited general AEs (days 0-28)			•	•				•	•	•	• [*]	•	• [*]	•	•	•	•
Unsolicited AEs (days 0-84)			•	•				•	•	•	• [*]	•	• [*]	•	•	•	•
Complete blood count ⁴ (2mL)	•	•						•	•		•		•	•	•	•	•
Biochemistry tests ⁵ (4mL)	•	•						•	•		•		•	•	•	•	•
PK samples (CAT tube) ⁶			•	•	•	•	•	•	•	• [*]	•	• [*]	•	•	•	•	•
ADA samples (CAT tube) ⁶			•								•		•		•	•	•
SMFA (CAT tube) ^{6,7}			•	•				•	•	• [*]	•	• [*]	•	•	•	•	•

Type of contact	Visit 1 (Screening)	Visit 2	Visit 3					Visit 4	Visit 5	Visit 5a*	Visit 6	Visit 6a*	Visit 7	Visit 8	Visit 9	Visit 10	Visit 11
Study Day	D-84 to D-1	D-1	D0	D0	D0	D0	D0	D1	D2	D4	D7	D10	D14	D21	D28	D56	D84
Time after D0 infusion			pre	EOI	1hr	3hr	6hr	24hr	48hr	96hr	Wk1	Wk1,5	Wk2	Wk3	Wk4	Wk8	Wk12
Safety Report ⁸											•						•
End of study visit																	•
Daily blood volume (mL)	13,5	6	34	24	10	10	10	30	30	24*	40	24*	40	30	40	34	30
Cumulative blood volume (mL)	13,5	19,5	53,5	77,5	87,5	97,5	107,5	137,5	167,5		207,5		247,5	277,5	317,5	351,5	381,5*

1. A physical examination including height and weight and vital parameters will be performed at the screening visit. At inclusion, a repeat measurement of body weight will be obtained. Additional measurements will take place at the discretion of the physician.
2. Vital signs including body temperature, blood pressure and pulse will be recorded at the screening visit. Additional measurements will take place at the discretion of the physician.
3. E.g. nasopharynx/throat swab for SARS-CoV-2 PCR, where required by current Radboudumc-wide or MC-specific guidelines. Symptom-driven diagnostics may also be performed at other visits.
4. CBC test includes: hemoglobin, hematocrit, platelets, red blood cell count, MCV, MCH, MCHC, white blood cell count + differentiation
5. Biochemistry test includes: creatinine, urea, sodium, potassium, bilirubin, AF, yGT, AST, ALT, LDH and hs-Trop-T. Blood will be collected in 2 lithium heparin tubes (2mL). Additional at screening: serology malaria (2mL), cholesterol, triglyceride and glucose (2mL).
6. Serum will be collected in 4mL or 10mL CAT tubes.
7. SMFA assays will be performed at 6 time points (Pre, EOI, D7, D28, D56, D84). Serum will be collected for optional/exploratory SMFA sampling time points on D1, D2, D4*, D10*, D14 and D21.
8. Safety report: A safety report for each group is prepared by the clinical investigator once the final subject in that group has completed 7 days of follow-up. A safety report of all the safety data is made after the close-out visit.

* Visit 5a and 6a will only be performed in group 5. The cumulative blood volume in group 5 is approximately 430 mL.

8.4 Withdrawal of individual subjects

Subjects can leave the study at any time for any reason if they wish to do so without any penalty or loss of medical benefits. Subjects can also be withdrawn from the study procedures at the discretion of the clinical investigator or the local safety monitor for urgent medical reasons or if exclusion criteria are met. The following reasons may lead to withdrawal of individual subjects:

- Withdrawal of informed consent by volunteer;
- Any serious adverse event;
- Any adverse event that, according to clinical judgment of the investigator, is considered as a definite contraindication to proceeding with the study procedures;
- Immunosuppressant or other immune-modifying drugs administered chronically (i.e., more than 14 days in total) during the study period. Topical steroids are allowed;
- Immunoglobulin and/or any blood products administered during the study period;
- Pregnancy;
- Completely lost to follow-up;
- Ineligibility (arising during the study or retrospectively, having been overlooked at screening);
- If the investigator or safety monitor believes that continuation would be detrimental to the subject's well-being;
- Volunteer non-compliance with study requirements;
- Any other protocol deviation that results in a significant risk to the subject's safety.

8.4.1 Handling of withdrawals

For subjects lost to follow-up (i.e. those subjects whose status is unclear because they fail to appear for study visits without stating an intention to withdraw), extensive effort (i.e. documented phone calls and e-mails) will be undertaken to locate or recall the volunteer or at least to determine his or her health status. The investigator should show "due diligence" by documenting in the source documents steps taken to contact the subject. In case of premature withdrawal for any reason, the investigator will exert his/her best effort to:

- Update any ongoing AE/SAEs that remained ongoing at the time of the subject's last visit prior to withdrawal.
- Conduct an interview to determine if the subject has had any reaction or AE (serious or non-serious) since the last visit. Where possible, the investigator should visibly or physically assess any reported adverse reaction or AE and document whether it led to the withdrawal.
- Conduct a physical examination.
- Collect blood for biochemical and hematological clinical laboratory parameters.
- Review the subject's memory aid if it is still in use at the time of withdrawal.
- Document the reason for premature withdrawal on the CRF.
- Update the subject's contact information.

8.4.2 **Withdrawals at specific time-points**

During screening

If the investigator ascertains that the subject does not meet the inclusion/exclusion criteria after the subject signs the informed consent form, the investigator only needs to note the reason for subject exclusion on the screening log.

As a result of erroneous inclusion

If a subject who does not meet the inclusion/exclusion criteria is inadvertently included in the trial, the investigator will terminate the subject's participation in the trial, the sponsor will be informed immediately prior to administration of study product and a protocol deviation will be completed. In the event that the study product has already been given, the subject will be encouraged to complete all remaining safety related follow-up visits and procedures through the last study visit. However, the subject's data will be excluded from the analysis.

As a result of withdrawal of informed consent

If a subject withdrawal occurs for any reason, the investigator must make every effort to determine the primary reason for a subject's withdrawal from the study and record this information in the study file. However, in accordance with the principles of the current version of the Declaration of Helsinki, a subject does have the right to withdraw from the study at any time and for any reason and is not obliged to give his or her reasons for doing so.

With permission of the subject, all data generated before withdrawal will be included in final study analysis with subject's permission, unless it is felt that the data is compromised. Blood samples collected before withdrawal will be used/stored unless the subject specifically requests otherwise.

As a result of occurrence of an adverse event/serious adverse event

If any subject develops an AE/SAE leading to premature withdrawal, the event will be fully followed-up. For premature withdrawal in connection with the emergence of an AE/SAE that is considered to be clinically relatively favorable (for example, the diagnosis is known, and it is expected to be resolved completely within a week), intermittent follow-up may be accepted as long as the plan for follow-up of the event is fully described in the notes section of the subject's CRF. Follow-up visits will be carried out for all subjects who are withdrawn due to occurrence of an AE or in connection with a change in any other safety indicator (vital sign or clinical laboratory result).

All data generated before withdrawal will be included in final study analysis with subject's permission, unless it is felt that the data is compromised. Blood samples collected before withdrawal will be used/stored unless the subject specifically requests otherwise.

As a result of lost to follow-up

To prevent lost to follow-up, subjects will be reminded by phone, email, or text message of their next study visit. In the event of a missed visit, subject will be contacted by phone within 1 day. A

subject who misses two consecutive visits and cannot be reached or located after 5 attempts will be considered lost to follow-up. Efforts to contact the subject will be documented in source documents. Any subject who fails to attend the final study visit will also be classified as lost to follow-up. There will be no replacement for subjects who are lost to follow-up. All data generated before withdrawal will be included in final study analysis with subject's permission, unless it is felt that the data is compromised. Blood samples collected before withdrawal will be used/stored unless the subject specifically requests otherwise.

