4.3 Exclusion criteria

Deviations from exclusion criteria are not allowed because they can potentially jeopardize the scientific integrity, regulatory acceptability of the study, or subject safety. Therefore, adherence to the criteria as specified in the protocol is essential. If any of the following exclusion criteria apply, the subject must not be included in the study:

1. Acute or chronic disease at time of TB31F administration, clinically significant pulmonary, cardiovascular, hepatic or renal functional abnormality, as determined by physical examination or laboratory screening tests:
 - a. Acute disease is defined as the presence of a moderate or severe illness with or without

fever. Subjects with a minor illness on the day of TB31F administration will be (temporarily) excluded from participation, but may be re-evaluated for inclusion at a later date. Subjects with a positive SARS-CoV2 test at inclusion will be (temporarily) excluded from participation but may be re-evaluated for inclusion at a later date (following current Radboudumc guidelines).

- b. Fever is defined as an oral, axillary or tympanic temperature $\geq 38.0^{\circ}\text{C}$ (100.4°F). The preferred route for recording temperature in this study will be oral.
- c. Any abnormal and clinically significant baseline laboratory screening tests of ALT, AST, creatinine, hemoglobin, platelet count or total white blood cell count, as defined in the protocol according to the FDA Toxicity Grading Scale for Healthy Adult and Adolescent Subjects Enrolled in Preventative Vaccine Clinical Trials (appendix 1).

2. History of malignancy of any organ system (other than localized basal cell carcinoma of the skin), treated or untreated, within the past 5 years.
3. Chronic use of i) immunosuppressive drugs, ii) antibiotics, iii) or other immune modifying drugs within three months prior to study onset (inhaled and topical corticosteroids and oral anti-histamines exempted) or expected use of such during the study period.
4. Positive urine toxicology test for cannabis, cocaine or amphetamines at screening or at inclusion.
5. Screening tests positive for Human Immunodeficiency Virus (HIV), active Hepatitis B Virus (HBV), Hepatitis C Virus (HCV).
6. Use of any investigational or non-registered product (drug or vaccine) during the study period other than the study product.
7. Participation in any other clinical study in the 30 days prior to the start of the study or during the study period.

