10.1 Primary study parameter(s)

The number of subjects enrolled, completed, or withdrawn will be summarized. Reasons for withdrawal, when known, will be provided. Demographic data will be summarized by descriptive statistics and will include total number of observations (n), mean, standard deviation (SD) and range for continuous variables, and number and percentages for dichotomous variables. The primary safety, and reactogenicity outcomes will include all subjects who meet the eligibility criteria, receive study product mAb TB31F, and for whom safety data are available.

Safety Analyses

For the safety analysis, data from all subjects who received a dose of mAb TB31F and for whom safety data are available will be included. All analyses will be descriptive. Data will be presented by dose, overall/dose and overall/subject. Results will be summarized by study group. The percentage of subjects with at least one local AE (solicited and unsolicited), with at least one general AE (solicited and unsolicited) and with any AE during the solicited follow-up period will be tabulated with exact 95% CI (two-sided). No multiplicity adjustment will be implemented in analysis. The same calculations will be performed for AEs rated as grade 3. The percentage of subjects reporting each individual solicited local and general AE during the solicited follow-up period will be tabulated with exact 95% CI. The same tabulation will be performed for grade 3 AEs and for AEs with relationship to mAb TB31F administration. The reports of unsolicited AEs will be reviewed by a physician and will be categorized by ICD-10. The percentage of subjects with at least one report of unsolicited AE and reported up to 28 days after mAb TB31F administration will be tabulated with exact 95% CI. The same tabulation will be performed for grade 3 unsolicited AEs and for unsolicited AEs with a relationship to mAb TB31F administration. SAEs will be described in detail. Withdrawals due to AEs/SAEs will also be summarized. Vital signs which are outside of the normal range and clinically significant will also be listed in tables. The frequency of signs and symptoms will be compared between groups with the chi-square test or fishers exact test. Serious adverse events (SAEs) occurring at any point during the trial will be summarized and relatedness to vaccine will be assessed.

Clinical Laboratory Data Analyses

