10.5 Accounting for Missing, Unused, and Spurious Data

The SAP will be followed even if data are missing. For the safety analysis, data from all subjects who received a dose of mAb TB31F in the study will be included. Subjects with missing data will not be imputed. Subjects who miss an appointment date will not be removed from the study. Rather, their appointment and laboratory values will be recorded by appropriate missing value notation in the clinical database. Non-analyzable data will be documented in the deviations.

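### The safety analysis set is defined in conflicting ways: some passages drop a dosed subject later found ineligible, others keep every dosed subject

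*Protocol*

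**What the plan says.** **Passages that leave out a dosed but ineligible subject**

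- Protocol 8.4.2, on erroneous inclusion, first keeps the follow-up: "In the event that the study product has already been given, the subject will be encouraged to complete all remaining safety related follow-up visits". It then says: "However, the subject's data will be excluded from the analysis". Safety is not excepted.
- The first paragraph of Protocol 10.1 makes meeting the eligibility criteria a condition for the primary safety and reactogenicity outcomes.
- The SAP, under Trial population, repeats that condition. It also requires efficacy and immunogenicity data.

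**Passages that keep the same subject**

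- Protocol 10.1, Safety Analyses: "data from all subjects who received a dose of mAb TB31F and for whom safety data are available will be included".
- Protocol 10.5: "For the safety analysis, data from all subjects who received a dose of mAb TB31F in the study will be included".

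**Context**

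- Section 8.4 lists this reason for withdrawal: "Ineligibility (arising during the study or retrospectively, having been overlooked at screening").
- The trial is open-label (8.2), and a dosed subject cannot be replaced (8.5).

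**Cannabis, a side issue**

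- Exclusion 4 in section 4.3 reads: "Positive urine toxicology test for cannabis, cocaine or amphetamines at screening or at inclusion".
- Section 8.3.12 excludes for amphetamines and cocaine without naming a visit, but its cannabis sentence begins: "A positive test for cannabis on the inclusion day prior to TB31F".

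**The concern.** The primary objective is reactogenicity and safety after one dose. An adverse event after TB31F is evidence about TB31F whether or not a criterion was overlooked, so exposure should decide who enters the safety tables.

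Ineligibility can surface after dosing, when the subject's events are already known to everyone in an open-label trial. Some criteria rest on judgement, such as illness on the day of administration (exclusion 1) and the investigator's general opinion (exclusion 15). A work-up of an event could reopen them. Membership of the analysis set could then depend on outcome, which would lower the reported rates.

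Erroneous inclusion is also the only case in 8.4.2 where a dosed subject's data are removed unconditionally. For withdrawn consent, withdrawal after an event and loss to follow-up, earlier data are kept with permission unless thought compromised.

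**Working it through.** **Step 1: the passages side by side.** Take a subject who received TB31F, has safety data, and is later found to have failed a criterion.

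| Place | Eligibility required? | Subject in the safety analysis? |
|---|---|---|
| Protocol 8.4.2, erroneous inclusion | yes | no |
| Protocol 10.1, first paragraph | yes | no |
| SAP, Trial population | yes | no |
| Protocol 10.1, Safety Analyses | no | yes |
| Protocol 10.5 | no | yes |

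No order of precedence settles this cleanly. The opening of Protocol section 10 sends the analyst to the SAP. The SAP's population requires eligibility, its withdrawal paragraph points to Protocol 8.4, and its paragraph on deviations points to Protocol 10.5.

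**Step 2: the plan's own figures.** Protocol 4.4 gives, for n = 20, a 90% chance of at least one event at a true rate of 10.87% and a 90% chance of none at 0.52%.

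- At least one event: 1 − 0.1^(1/20) = 10.87%.
- No events: 1 − 0.9^(1/20) = 0.53% (0.525%, printed truncated as 0.52%).

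Both reproduce, so no sample-size figure is in error.

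**Step 3: precision lost if one dosed subject is dropped.** The true rate at which there is a 90% chance of at least one event is 1 − 0.1^(1/n).

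| Set | All dosed kept | One dropped |
|---|---|---|
| One group | n = 5: 36.9% | n = 4: 43.8% |
| Intravenous groups | n = 20: 10.87% | n = 19: 11.41% |
| All groups | n = 25: 8.80% | n = 24: 9.15% |

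**Step 4: the effect on a reported rate.** Section 10.1 asks for exact two-sided 95% intervals (Clopper-Pearson). Suppose the dropped subject had the only event.

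| Set | Kept | Dropped |
|---|---|---|
| One group | 1/5 = 20% (0.5% to 71.6%) | 0/4 = 0% (0% to 60.2%) |
| Intravenous groups | 1/20 = 5% (0.1% to 24.9%) | 0/19 = 0% (0% to 17.6%) |
| All groups | 1/25 = 4% (0.1% to 20.4%) | 0/24 = 0% (0% to 14.2%) |

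The direction depends on who is dropped. If the dropped subject had no event and another subject in the group did, 1/5 = 20% becomes 1/4 = 25%. The bias is downward only if removal is linked to having an event.

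**The case against.** **All-dosed is not the plan's sole definition.** A reader might infer that 8.4.2 alone breaks an otherwise settled all-dosed safety analysis. The documents do not support that. Section 8.4.2 agrees with the first paragraph of 10.1 and with the SAP, and the SAP is the document that section 10 says governs the analysis. This objection stands. It widens the problem to conflicting definitions, and a repair of 8.4.2 alone would leave the exclusion in place.

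**Nothing is deleted.** A reader might take the rule to mean that a subject's safety record is lost. It removes data from the analysis only. Dosed subjects are followed until their events resolve or stabilise (9.5.4), events are listed by participant and SAEs summarised (10.1), the safety committee assesses all participants at the end (9.5.3), and the holding rules carry no eligibility condition. This stands: the tabulated rates are what is exposed.

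**The numerical example is a worst case.** It needs an erroneous inclusion and needs that subject to have the group's only event. The documents give no probability for either. The intervals overlap heavily and the safety analyses are described as descriptive. The interim summary in 13.2 counts all 20 intravenous subjects, so none had been dropped by then. All of this stands, although a later retrospective finding remains possible.

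**The link between events and removal is conjecture.** No passage says that work-ups of events will uncover ineligibility. The rule permits outcome-dependent removal; the documents do not show that it occurs.

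**The cannabis mismatch should not carry the argument.** A reader might infer that 8.3.12 would lead the site to dose a subject whom 4.3 excludes. But 8.3.12 never permits a screening positive; it only ties its stated cannabis exclusion to the inclusion day. Sections 4.1, 4.3 and 8.3.3 require all criteria to be checked at both visits, forbid deviations and invite back only eligible subjects, which would ordinarily stop such a case. The difference is one of wording, by implication, and separate from the analysis set.

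**Conclusion.** The contradiction is real and sits in the primary analysis. For a dosed subject later found ineligible, three passages say out and two say in. An analyst following 8.4.2 as written would leave known adverse events out of the primary safety tables.

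The size is modest overall. One lost subject moves the rate detectable with 90% chance from 10.87% to 11.41% over the intravenous groups, and from 36.9% to 43.8% within a group. The more serious consequence is that an event can vanish from a group's result, at worst 1/5 becoming 0/4. That assumes one erroneous inclusion and that this subject had the only event. The conflict between the passages depends on neither assumption.

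The documents do not show that rates have been or will be biased, or that safety oversight is weakened. The cannabis wording is a minor separate matter; which rule should apply is for the sponsor to settle.

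**What to change.** 1. **One safety set.** State identically in Protocol 8.4.2, 10.1, 10.5 and the SAP that the safety set is all subjects who received TB31F, regardless of eligibility.
2. **Protocol 8.4.2.** Replace the exclusion sentence with, for example: *A subject who has received TB31F stays in the safety analysis; the eligibility deviation is listed.*
3. **Protocol 10.1, first paragraph, and SAP, Trial population.** Delete the eligibility condition from the safety set in both. The SAP's requirement for efficacy and immunogenicity data is a different restriction in the same sentence, but it too must go if one all-dosed set is to hold.
4. **PK and SMFA sets.** Confine any eligibility-based exclusion to these. Decide it from the nature of the deviation before the results are seen. Section 13.2 already reports preliminary PK and SMFA findings, so the criteria should be written down now.
5. **Separately:** reconcile exclusion 4 in 4.3 with 8.3.12 on a positive cannabis test at screening.

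The cost is a few sentences in the protocol and one in the SAP. No new data are needed, because 8.4.2 already provides for safety visits to continue in these subjects.
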